### Design:

- This is a prospective, single institution, single arm, multi-cohort phase II study of sunitinib in subjects with recurrent gliosarcoma and primary CNS sarcoma that have failed prior surgery and irradiation (unless radiation therapy was contraindicated).
- Subjects will be classified into three cohorts: 1) Primary gliosarcoma; 2) Secondary gliosarcoma; 3) Primary CNS sarcoma. Cohort expansion will be carried out at indication of promising response.
- Sunitinib will be administered orally using a continuous schedule at 50 mg per day (with dose adjustments allowed for toxicity) for 2 weeks with 1 week off to constitute a 3-week cycle until disease progression or development of intolerable side-effects.
- Toxicity will be assessed every cycle by CTCAE version 5.0.

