### **3.2 DRUG ADMINISTRATION**

Sunitinib 50 mg will be self-administered orally, once daily on an outpatient basis. Sunitinib will be administered at a dose of 50 mg daily for 2 consecutive weeks followed by 1 week of rest. Studies in patients with metastatic renal cell carcinoma, sunitinib tolerability was superior with the 2-weeks on and 1-week off compared to 4-weeks on and 2-weeks off.[\[13, 14\]](#) Patients should be instructed to store sunitinib at room temperature. Patient will take sunitinib once daily, with or without food, as desired. Patients should drink plenty of water or take rehydration fluids to avoid dehydration if diarrhea occurs. Patients should be alerted to the possibility that sunitinib capsules can cause a yellow discoloration of the skin on direct contact. If this happens, the patient should wash immediately with soap and water. Thyroid function will be monitored at baseline and at every two cycles. Dose reductions (to 37.5 mg and then 25 mg) will be permitted for patients experiencing grade 3 or 4 sunitinib-related toxicities.

**Abbreviated Title:** Ph II Sunitinib CNS Sarcomas

**Version Date:** 05-30-18

Because hypertension is a known and potentially serious but rare adverse event associated with sunitinib treatment, patients will have their blood pressure monitored and recorded at baseline and weekly during treatment including the weeks off the investigational drug either at the doctors' office or using any calibrated electronic device.

All subjects will be evaluated with magnetic resonance imaging at baseline and after every 2 cycles of treatment. Patients will continue treatment until there is disease progression or development of intolerable side effects.

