### 3.3 DOSE MODIFICATIONS

Dose reductions (to 37.5 mg and then 25 mg) will be permitted for patients experiencing grade 3 or 4 sunitinib-related toxicities. If treatment is delayed for more than 4 weeks due to treatment associated toxicity, the patient will be discontinued from treatment and followed until disease progression.

- Patients may continue to receive therapy provided the following criteria are met on day 1 of each cycle:
  - ANC  $\geq 1.0 \times 10^9/L$
  - Platelets  $\geq 75 \times 10^9/L$
  - Non-hematological toxicity recovered to < grade 2 (or tolerable grade 2 or baseline)
  - No evidence of progressive disease
- With development of adverse events possibly related to sunitinib, dose reduction is permitted (see guideline below). If an adverse event is not covered by the guideline, dose may be reduced or held at the discretion of the investigator for the subject's safety. Subjects with adverse events that are manageable with supportive therapy may not require dose reductions (e.g. nausea/vomiting may be treated with antiemetics, diarrhea may be treated with loperamide, and electrolyte abnormalities may be corrected with supplements rather than by dose reduction).
- If a patient takes 75% or more of scheduled doses during a cycle, missed doses will not be reported as deviations. If the study team instructs a patient to hold the investigational drug, it will not be considered a protocol deviation.
- Increase in BP has been reported with use of anti-VEGF agents. Guidelines for management [15] is provided in Appendix 13.5

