### 3.5 STUDY CALENDAR

Procedure	Screening/ Baseline	Cycle 1			Subsequent Cycles		End of treatment Visit 	Post Therapy Follow- up
		Day 1	Day 8	Day 15	Day 1	Day 15		
		+/- 3			+/- 3	+/-3		
History and PE	X	X	X		X		X	
Vital signs	X	X	X		X		X	
Performance Score (KPS)	X	X	X		X		X	X
CBC w/diff, plts	X	X	X		X		X	
Serum chemistry 	X	X	X		X		X	
Urinalysis	X							
PT/PTT INR	X							
Thyroid function tests 	X				X		X	
β-HCG (serum or urine)	X							
Blood Pressure	X	X	X	X	X	X	X	
Correlative Research Studies 		X	X		X		X	
MDASI-BT 	X						X	
Cranial MRI/CT 	X						X	
EKG/ECHO 	X							
Adverse Events 		X					→	
Concomitant Medications 	X	X			X			
Actigraphy 	X	X	X	X	X	X		
NIH Advanced	X							

*Abbreviated Title: Ph II Sunitinib CNS Sarcomas*

*Version Date: 05-30-18*

Procedure	Screening/ Baseline	Cycle 1			Subsequent Cycles		End of treatment Visit 	Post Therapy Follow- up
		Day 1	Day 8	Day 15	Day 1	Day 15		
Directives Form 								

*Total protein, albumin, calcium, phosphorus, magnesium, glucose, BUN, creatinine, sodium, potassium, alkaline phosphatase, ALT, AST, total bilirubin, direct bilirubin*

*Thyroid function tests to be done at baseline, C2D1, D1 of every other cycle and at end of treatment visit*

*Blood for correlative studies will be collected at C1D1, C1D8, C2D1 and at end of treatment visit*

*MDASI-BT to be done at baseline, at time of imaging studies throughout treatment, and at end of treatment visit*

*Response assessment to be done every other cycle within 7 days of initiation of odd numbered cycles, starting with Cycle 3 and at end of treatment visit. (Pre C1 MRI is done at screening. MRI is preferred.)*

*ECHO to be done at screening, day 1 of cycle 3 and every other cycle EKG/ECHO frequency of day 1 of the third cycle and every other cycle.*

*Adverse Event and Concomitant Medication evaluations to be documented at day 1 of each cycle and at end of treatment visit*

*ActiGraphy to be done at baseline and during cycles 1 through 6*

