### 6.3.4 Progression-Free Survival

PFS is defined as the duration of time from start of treatment to time of progression or death, whichever occurs first. In cases where this might be unclear, patients may continue on trial.

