### 6.3.5 Response Review

All subjects will be evaluated by cranial imaging every 6 weeks.

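### Response scans follow cycle starts in 3.2 and 3.5 but a 6-week interval in 6.3.5; if the calendar governs, toxicity delays shift progression dating and raise 6-month PFS modestly on average

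*Combined protocol and SAP*

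**What the plan says.** Three places set the imaging schedule for patients on treatment.

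- Section 3.5, footnote 5: "Response assessment to be done every other cycle within 7 days of initiation of odd numbered cycles", beginning with Cycle 3.
- Section 3.2: "All subjects will be evaluated with magnetic resonance imaging at baseline and after every 2 cycles of treatment".
- Section 6.3.5: "All subjects will be evaluated by cranial imaging every 6 weeks". It gives no anchor date and no window.

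The Précis sets the nominal cycle: "for 2 weeks with 1 week off to constitute a 3-week cycle". Cycle starts can move, because section 3.3 says "Patients may continue to receive therapy provided the following criteria are met on day 1 of each cycle", the criteria being blood counts, recovery from non-hematological toxicity and absence of progression. The same section limits a single delay: "If treatment is delayed for more than 4 weeks due to treatment associated toxicity, the patient will be discontinued from treatment". It states no limit on the total of several delays.

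Section 6.3.4 defines the endpoint: "PFS is defined as the duration of time from start of treatment to time of progression or death, whichever occurs first". Section 8.3 estimates PFS by Kaplan-Meier and gives no rule for scans that come early or late. Six-month and median PFS are secondary objectives (1.1.2), and 8.1 names PFS as an example of the clinical considerations weighed in a go/no-go decision.

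**The concern.** With imaging tied to cycle starts, a toxicity delay also delays the next look at the tumour. Two patients whose tumours progress on the same day can then have different progression dates because one had a dose delay. The Cycle 9 scan is nominally only about two weeks before the 6-month mark, so a fairly short total delay carries it across. A patient who has already progressed since the previous scan is then counted as progression-free at 6 months.

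The trial has a single arm, so there is no concurrent control in which this could cancel. Delays are foreseeable: 11.2.2 reports grade 3-5 treatment-related events in 60.3% of subjects with other solid tumours, and the table in 3.3.1 calls for holds for several toxicities. At stake is whether recorded PFS partly reflects how often treatment was delayed.

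**Working it through.** **Reproducing the stated interval.** Two cycles of 21 days make 42 days, or 6 weeks. The schedules therefore coincide when every cycle starts on time.

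**Scan dates under the calendar rule.** The scan for cycle k falls on day 21 × (k − 1) + D, where D is the cumulative delay up to that cycle's start. Six months is taken as 182.6 days (26.09 weeks).

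| Delay | C3 | C5 | C7 | C9 | Last scan by 6 months |
|---|---|---|---|---|---|
| None | 42 | 84 | 126 | 168 | 168 (week 24) |
| 14 days before C3 | 56 | 98 | 140 | 182 | 182 (week 26) |
| 21 days before C3 | 63 | 105 | 147 | 189 | 147 (week 21) |
| 21 days before C9 | 42 | 84 | 126 | 189 | 126 (week 18) |
| 28 days before C3 | 70 | 112 | 154 | 196 | 154 (week 22) |
| 28 days before C9 | 42 | 84 | 126 | 196 | 126 (week 18) |
| 28 days before C3 and again before C5 | 70 | 140 | 182 | 224 | 182 (week 26) |

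- One 28-day delay lengthens the gap it falls in from 42 to 70 days.
- The Cycle 9 scan passes 6 months once the cumulative delay reaches 15 days (168 + 15 = 183). With the 7-day window the scan itself may fall on days 161 to 175 before any delay, so the threshold runs from about 8 days (175 + 8 = 183) to 22 days (161 + 22 = 183).

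**Effect on one patient's counted 6-month PFS.** The documents give no median PFS, so medians of 8, 12 and 18 weeks are assumed, with exponential PFS: S(t) = 2^(−t/median). If progression is seen only at scheduled scans, the chance of being counted progression-free at 6 months is S at the last scan before that date. At a 12-week median with no delay it is 2^(−24/12) = 25.0%.

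| Median (weeks) | No delay, S(24) | 1 week, S(25) | 2 weeks, S(26) | 3 weeks, by C7, S(21) | 3 weeks, before C8 or C9, S(18) |
|---|---|---|---|---|---|
| 8 | 12.5% | 11.5% | 10.5% | 16.2% | 21.0% |
| 12 | 25.0% | 23.6% | 22.3% | 29.7% | 35.4% |
| 18 | 39.7% | 38.2% | 36.7% | 44.5% | 50.0% |

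A cumulative delay of 1 or 2 weeks lowers the counted figure, because the Cycle 9 scan moves closer to 6 months while staying before it. A 3-week delay raises it by about 4 to 10 points.

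**Effect on a cohort.** The delay frequency is also not given. Each cycle start was assumed to be delayed with probability 0, 5, 10 or 20%, by a uniform 1 to 4 weeks. Simulated 6-month PFS:

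| Median (weeks) | 0% | 5% | 10% | 20% |
|---|---|---|---|---|
| 8 | 12.4% | 13.4% | 13.9% | 14.7% |
| 12 | 25.0% | 26.0% | 26.9% | 27.8% |
| 18 | 39.7% | 40.7% | 41.6% | 42.4% |

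The average shift is +1.0 to +2.8 points. In the 5, 10 and 20% scenarios, about 11, 17 and 22% of patients have their last scan before 6 months later than week 24 and so are shifted downward.

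**Sensitivity.** If instead 20 to 60% of patients have one maximal 28-day delay, with medians of 2 to 6 months, the shift is +0.5 to +6.3 points. The top of that range requires 60% of patients to be delayed, all just before Cycle 8 or 9.

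All shifts are relative to an undelayed 6-week schedule. That schedule has its own lag: at a 12-week median the true value is 2^(−26.09/12) = 22.2%, against 25.0% counted.

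**The case against.** A reader might infer that the error is always upward, or that every delayed patient has progression dated late. Neither follows. The 1- and 2-week columns above go down, and shifted scans can catch some progression sooner: with 28 days of delay before Cycle 7, progression on days 127 to 154 is dated day 154 rather than 168. Only the average upward shift stands.

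A reader might also infer that 6.3.5 plainly intends a fixed calendar clock. It is one sentence without an anchor or window and may only restate two nominal cycles. What stands is that the documents do not say which rule governs when a cycle slips.

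The calculation overstates the effect to the extent that events are not dated by scheduled scans. Deaths are not. The RANO table in 6.3.3 lets clinical decline alone establish progression, and the calendar has history, examination and performance status on Day 1 of each cycle. If 30% of events were dated exactly (an assumption), the shift at a 12-week median would fall from about +1.1 to +2.8 points to about +0.8 to +2.0 (× 0.7). This reduces the problem but does not remove it, since no scan is required at every cycle.

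The shift is also small beside sampling error. With 32 patients and 6-month PFS of 25%, the standard error is √(0.25 × 0.75/32) = 7.7 points, a 95% half-width of about 15. PFS is secondary and descriptive, and 8.1 brings it in only as an example, after a response boundary has not been exceeded. That limits the weight of the point. The inconsistency still has to be settled, because it decides when a delayed patient is scanned.

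**Conclusion.** The inconsistency is real: 3.2 and 3.5 give one scan date for a delayed patient and 6.3.5 gives another. If the study calendar is followed, progression dating depends on toxicity delays, in either direction for an individual and upward on average for 6-month PFS. The size is about 1 to 3 points per cohort, and less where decline or death dates the event. It rests on exponential PFS, medians of 8 to 18 weeks and a 5-20% delay probability per cycle, none of which the documents supply. The shift in median PFS was not quantified.

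This is a modest average bias in secondary endpoints and in the PFS input to the go/no-go review. It would be tempting to extend it to the response-rate stopping boundaries in 8.1, but no effect on them is shown. The change is worth making because it is cheap and removes an avoidable link between toxicity and recorded PFS.

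**What to change.** Reconcile 3.2 and footnote 5 of 3.5 with 6.3.5. State in all three places that response imaging in patients on treatment is scheduled every 6 weeks in calendar time from Cycle 1 Day 1 (weeks 6, 12, 18, 24 and so on, within 7 days) and is not shifted by delayed cycle starts. Leave the dosing and treatment-stopping rules as they are.

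The cost is a wording change, with no more imaging than 6.3.5 already calls for. For delayed patients some scans will no longer coincide with a Day 1 visit. The MDASI-BT, which 3.4 and 3.5 tie to imaging, would move with them. The ordinary lag of a 6-week schedule remains, but it would no longer depend on how often treatment was delayed.

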### 3.6 CRITERIA FOR REMOVAL FROM PROTOCOL THERAPY AND OFF STUDY CRITERIA

Patients may be removed from the protocol therapy and/or study at any time at their own request or may be withdrawn at the discretion of the investigator for safety, behavioral or administrative reasons.

Prior to removal from study, effort must be made to have all subjects complete a safety visit approximately 30 days following the last dose of study therapy. The following evaluation will occur:

- KPS
- Adverse Event assessment
- Physical examination
- Vital signs and weight
- CBC with differential, comprehensive chemistry panel, thyroid function tests

*Abbreviated Title: Ph II Sunitinib CNS Sarcomas*

*Version Date: 05-30-18*

- Cranial imaging
- Blood collection for correlative studies
- MDASI-BT

### 3.6.1 Criteria for Removal from Protocol Therapy

The reason(s) for discontinuation must be clearly documented and may include:

- Patient voluntarily withdraws from treatment (follow-up permitted)
- Completion of protocol therapy
- Progressive disease
- Unacceptable toxicity as defined in section [3.3](#)
- Investigator discretion
- Positive pregnancy test
- Treatment is delayed for more than 4 weeks due to treatment associated toxicity.

### 3.6.2 Off-Study Criteria

- Completed study follow-up period
- Participant requests to be withdrawn from study (no follow-up permitted)
- Death

### 3.6.3 Off Protocol Therapy and Off-Study Procedure

Authorized staff must notify Central Registration Office (CRO) when a subject is taken off protocol therapy and when a subject is taken off-study. A Participant Status Updates Form from the web site (<http://home.ccr.cancer.gov/intra/eligibility/welcome.htm>) main page must be completed and sent via encrypted email to: NCI Central Registration Office [[contact]](mailto:[contact]).

## 4 CONCOMITANT MEDICATIONS/MEASURES

- All prescription and over-the-counter medications at trial entry as well as any new medications started during the trial must be documented. Patient may use any ongoing medications not prohibited by the protocol.
- No other anti-cancer therapy agents are permitted while the patient is on this trial.
- Corticosteroids (inducer of CYP3A4) may be used for control of sign and symptoms of increased intracranial pressure and must be recorded. If the dose is increased during the period of 5 days before scheduled cranial imaging, the study should be delayed by at least 2 weeks.
- Use of drugs with potential proarrhythmic actions should not be used.

**Abbreviated Title:** Ph II Sunitinib CNS Sarcomas

**Version Date:** 05-30-18

- Sunitinib is primarily metabolized by liver enzymes, in particular CYP3A4. Patients must not have taken potent inhibitors (azole antifungals such as ketoconazole/itraconazole; clarithromycin; erythromycin; diltiazem; verapamil) or inducers (rifampin; rifabutin; carbamazepine; phenobarbital; phenytoin; St. John's wort) of CYP3A4 enzyme within 7 and 12 days prior to drug administration respectively. Also during the study, potent inhibitors and inducers should not be administered. If usage is necessary, this must be discussed with a study team member and outcome of the discussion should be documented.
- Aprepitant, grapefruit juice, fluconazole, and voriconazole are moderate CYP3A4 inhibitors that should be avoided if possible, or used with caution.
- Ondansetron and related drugs are not recommended since they may interfere with the metabolism of sunitinib.
- Drugs known to cause prolongation of QTc should be avoided.

## 5 BIOSPECIMEN COLLECTION

### 5.1 CORRELATIVE STUDIES FOR RESEARCH

Test/assay	Volume blood (approx)	Type of tube	Collection point (+/- 48hrs)	Location of specimen analysis
Circulating mature endothelial cells and endothelial progenitor cells Immune-monitoring	8 ml at C1D1, C1D8, C2D1	CPT citrate (blue/black)	C1D1, C1D8, C2D1 and at end of treatment visit	[name] Lab
Circulating tumor cells	7.5 ml at C1D1, C1D8, C2D1	CellSave tube	C1D1, C1D8, C2D1 and at end of treatment visit	[name] Lab
Immune subset analyses	8 ml at C1D1, C1D8, C2D1	CPT citrate (blue/black)	C1D1, C1D8, C2D1 and at end of treatment visit	[name] Lab

For [name] Lab samples, contact the lab by email: [name] ([[contact]](mailto:[contact])), [name] ([[contact]](mailto:[contact])), [name] ([[contact]](mailto:[contact])), and [name]

*Abbreviated Title: Ph II Sunitinib CNS Sarcomas*

*Version Date: 05-30-18*

([[contact]](mailto:[contact])) when the patient is scheduled and by phone at [contact] when the blood has been drawn, and a [name] Lab member will come to pick it up. Store at ambient temperature. The samples will be 2D barcoded, securely stored at the appropriate temperature, and entered into a secure patient database that can only be accessed by laboratory members. Each laboratory member can only interact with the database at their approved level of access. All laboratory members have completed courses in patient information security and computer security. Samples will only be released with approval of the Principal Investigator. No cell lines will be established.

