### 1.2.5 Rationale for Exploratory Studies

Serum markers of angiogenesis: A potential mechanism for sunitinib resistance is the upregulation of alternative proteins and/or pathways that could drive tumor angiogenesis and/or growth independent of VEGF. Preclinical studies, involving RCC and non-RCC models have identified a variety of candidate proteins that may be involved in resistance to VEGF therapy. Among these proteins which stimulate angiogenesis directly or indirectly are fibroblast growth factor (FGF), hepatocyte growth factor (HGF), and placental growth factor (PlGF). We propose to explore the potential utility of these proteins as biomarkers of pharmacological and clinical activity of sunitinib in CNS sarcomas. These assays will be performed in the [name] Laboratory, DTB, NCI.

Peripheral blood immune monitoring: In addition to modulation of angiogenic activity, sunitinib also appears to regulate key anti-tumor immune response. Sunitinib has been shown to decrease the frequency of regulatory T cells (Tregs) and myeloid-derived suppressor cells (MDSCs) in metastatic renal cell carcinoma patients.[8, 9] It has been shown that development of sunitinib resistance is partly mediated by the survival of MDSCs, thereby providing sustained immune suppression and angiogenesis.[10] Sunitinib has also shown to shift T-helper cells toward a T helper 1 (Th1)-polarized response and increase the Th1 cell / T helper 2 (Th2) cell ratio. A significant decrease in the Th1/Th2 ratio was seen after sunitinib treatment in the PFS-short group in mRCC.[9, 11] Exhausted CD8+ T cells which express inhibitory receptors PD-1 and Tim-3 were found in cancer patients, and therapeutic response was correlated with decline in Tim-3+ CD8+ T cells. Peripheral blood will be collected into one 8 ml CPT tube. Peripheral blood mononuclear cells (PBMC) will be assessed using multiparameter flow cytometry for immune subsets including but not necessarily limited to CD8+ T-cells, CD4+Foxp3- T-cells, Tregs, monocyte subsets, MDSC subsets. Assessment will include functional markers, i.e. PD-1, Tim-3, CTLA-4, PD-L1, HLA-DR and/or CD40. Therefore, monitoring immune subsets in CNS sarcoma patients pre- and post-sunitinib therapy may contribute to improved understanding of sunitinib and possibly inform future studies.

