### 2.4 BASELINE EVALUATION

All baseline evaluation procedures should be done prior to the study treatments. They do not need to be repeated if performed within 28 days prior to study drug initiation.

- A complete history and physical [including baseline blood pressure measurement and determination of Karnofsky Performance Score (KPS)] examination.
- A baseline standard NOB Gd-DPTA enhanced MRI should be performed.
- Thyroid Function Tests (and subsequently every 2 cycles)
- Urinalysis
- MDASI-BT
- Correlative Studies Blood Collection

The MDASI-BT will be completed only by the patient, unless changes in vision or weakness make this difficult. If this occurs, then the caregiver or research assistant may read the questions to the patient or assist with marking the severity number or score as described by the patient. A caregiver may complete the questionnaires as a patient proxy if the patient's deficits preclude self-report; however, this must be done at every assessment from baseline to end of treatment. Non-English-speaking patients will complete the questionnaire with the assistance of an interpreter during the clinic visit.

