*End of treatment visit will occur approximately 30 days after the last dose of study drug. If the patient cannot return to the Clinical Center for this visit, a request will be made to collect required clinical labs from a local physician or laboratory. If this is not possible, patients may be assessed by telephone for symptoms.*

*As indicated in section 10.5, all subjects  $\geq$  age 18 will be offered the opportunity to complete an NIH advanced directives form. This should be done preferably at baseline but can be done at any time during the study as long as the capacity to do so is retained. The completion of the form is strongly recommended, but is not required.*

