**[contact] [contact]**

**Title: Phase II Study of Sunitinib in Sarcomas of the Central Nervous System**

#### **PILL and BLOOD PRESSURE DIARY FOR SUNITINIB**

**Days 1 – 14 of each cycle (1 Cycle = 21 days)**

Today's date: \_\_\_\_\_

Cycle Number: \_\_\_\_\_

Patient Name (or initials): \_\_\_\_\_

Patient Study ID: \_\_\_\_\_

**Abbreviated Title:** Ph II Sunitinib CNS Sarcomas

**Version Date:** 05-30-18

Sunitinib Dose/Frequency: _____ mg/day  Route: Oral Daily				BLOOD PRESSURE  BASELINE  WEEKLY			
DAY #	DATE-	TIME	INITIALS	Blood Pressure	DATE	TIME	INITIALS
1							
2							
3							
4							
5							
6							
7							
8							
9							
10							
11							
12							
13							
14							

**Abbreviated Title:** Ph II Sunitinib CNS Sarcomas

**Version Date:** 05-30-18

DAY #	DATE	TIME	INITIALS	Blood Pressure	DATE	TIME	INITIALS
15	Off day						
16	Off day						
17	Off day						
18	Off day						
19	Off day						
20	Off day						
21	Off day						

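### The correlative blood windows are not tied to dosing: C2D1 mixes rest-week and re-dosed samples, section 5.1 omits the pre-dose rule for C1D1, and the last sample is about 30 days off drug

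*Combined protocol and SAP*

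**What the plan says.** - **Draw times.** Section 5.1 sets the collection points as "C1D1, C1D8, C2D1 and at end of treatment visit", under the column heading "Collection point (+/- 48hrs". It does not say whether any draw is before or after that day's dose.
- **Calendar.** Footnote 3 of section 3.5 gives the same four points: "Blood for correlative studies will be collected at C1D1, C1D8, C2D1 and at end of treatment visit". The correlative row is marked at cycle 1 day 1 and blank under Screening/Baseline. The calendar's own day 1 window is +/-3 (no unit is legible; I take it as days).
- **Baseline.** Section 2.4 includes correlative blood in its list and states: "All baseline evaluation procedures should be done prior to the study treatments".
- **Dosing.** Section 3.2 has sunitinib taken "daily for 2 consecutive weeks followed by 1 week of rest". The diary in Appendix 13.2 confirms doses on days 1 to 14 and off days 15 to 21 ("1 Cycle = 21 days").
- **Last draw.** Calendar footnote 9: "End of treatment visit will occur approximately 30 days after the last dose of study drug". Section 3.6 places correlative blood at this visit. No draw is scheduled between C2D1 and this one.
- **Purpose.** Section 1.2.5 motivates the blood markers partly by mechanisms of sunitinib resistance, including survival of myeloid-derived suppressor cells, and partly by "monitoring immune subsets in CNS sarcoma patients pre- and post-sunitinib therapy".
- **Analysis.** Section 8.3 relates biomarkers to response by Spearman correlation, regression, Wilcoxon and t tests. Time since last dose does not appear.

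**The concern.** Section 1.1.3 wants changes in circulating markers. With a two-weeks-on, one-week-off schedule, a change can be read only if it is known whether each sample was taken on drug, off drug or just after restarting. A symmetric window around the first day of a cycle straddles exactly that boundary. A C2D1 difference between responders and non-responders could then partly reflect which side of the dose the blood was drawn.

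The final draw raises a different problem. A marker that rises because the tumour has escaped the drug, and one that rebounds because the drug has been stopped, look alike in a sample taken a month after the last dose. The disease is rare and mistimed samples cannot be collected again.

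**Working it through.** The plan states no figure on this point, so there is none to reproduce. The check lays the windows over the dosing schedule.

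**Inputs.** Doses on days 1 to 14 of a 21-day cycle (section 3.2, Appendix 13.2); window +/-48 h (section 5.1); final visit about 30 days after the last dose (section 3.5, footnote 9). Cycle 2 day 1 is study day 21 + 1 = 22 if there is no delay.

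**Step 1: windows against dosing**

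| Draw | Study days at +/-48 h | Dosing state |
|---|---|---|
| C1D1 | 2 days before to day 3 | Pre-dose if section 2.4 is applied; on section 5.1 alone, up to 3 doses taken |
| C1D8 | 6 to 10 | On drug every day |
| C2D1 | 20 to 24 | Days 20-21 and a pre-dose day 22 draw: off drug. Post-dose day 22 to day 24: 1 to 3 cycle 2 doses |
| End of treatment | about 28 to 32 days after last dose | Off drug |

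For C2D1 the off-drug part lies 20 - 14 = 6 to 22 - 14 = 8 days after the last cycle 1 dose. The re-dosed part includes doses on days 22, 23 and 24. With the calendar's +/-3 days the span widens to days 19 to 25.

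Section 3.3 also tolerates toxicity delays of up to 4 weeks. If C2D1 follows the actual restart, the off-drug interval could reach 8 + 28 = 36 days.

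**Step 2: what this means for exposure (illustration only).** The documents give no half-life, so I assume h = 1 to 7 days and simple exponential decline. Fraction of drug remaining t days after the last dose = 0.5^(t/h).

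| t (days) | h = 1 | h = 5 | h = 7 |
|---|---|---|---|
| 6 | 1.6% | 43.5% | 55.2% |
| 8 | 0.4% | 33.0% | 45.3% |
| 30 | <0.1% | 1.6% | 5.1% |

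Across the assumed range the final sample is essentially off drug.

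**Step 3: spread of exposure within the C2D1 window.** Treat daily dosing as continuous input for 14 days, then 7 days off, and express the level as a share of steady state.

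- Just before the first cycle 2 dose: (1 - 0.5^(14/h)) x 0.5^(7/h).
- 48 h later: that level x 0.5^(2/h) + (1 - 0.5^(2/h)).

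h = 5: 0.856 x 0.379 = 0.32; then 0.32 x 0.758 + 0.242 = 0.49.

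h = 1: 1.00 x 0.0078 = 0.008; then 0.008 x 0.25 + 0.75 = 0.75.

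The spread is about 32% to 49% of steady state at a 5-day half-life and about 1% to 75% at 1 day. The mixing of dosing states is certain from the schedule. How far it moves exposure depends on a half-life that the documents do not give.

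**The case against.** The strongest reply is that much of this is already handled. Section 2.4 puts correlative blood before treatment, and a pre-dose C1D1 draw satisfies sections 2.4, 5.1 and the calendar together. For C2D1, section 3.3 requires blood counts to meet criteria on day 1 before therapy continues, and the calendar puts those counts and the research tubes at the same visit, so pre-dose collection is the natural practice. The diary has date and time columns for each dose, which might allow samples to be classified afterwards. The final draw fits the stated pre/post comparison, and no section says that this sample is there to show resistance.

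Most of this is fair, and it rules out several stronger inferences:

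- **That the baseline may legitimately follow three doses.** Only if section 2.4 is ignored. The fault is that the specimen table and calendar do not repeat its rule.
- **That drug effect cannot be estimated at all.** The whole C1D8 window is on drug, so an early change from a pre-dose baseline is estimable.
- **That C2D1 spans almost the full range of exposure.** Step 3 shows otherwise at a 5-day half-life.
- **That the final sample is selectively missing in the fastest progressors, or taken after a new therapy.** Footnote 9 does allow local clinical laboratory tests or a telephone call for those who cannot return. But section 3.6 asks for effort to have all subjects complete the visit, and section 4 bars other anti-cancer agents while on trial, without saying whether that covers the period after treatment stops. Both outcomes are possible; neither is shown.

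What the reply does not answer is C2D1. Usual practice is not a rule for the research tube, section 5.1 does not require a draw time, and section 8.3 does not use time since last dose. Nor does it supply a sample near progression.

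**Conclusion.** The point holds in limited form, in three parts.

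1. **C2D1** is defined over study days 20 to 24 and can be off drug or up to three doses into cycle 2 under the same label. This follows from the documents without further assumption.
2. **C1D1** is governed by sections that do not say the same thing: before treatment (2.4), +/-48 h (5.1), and the calendar's C1D1 mark with +/-3 days and a blank baseline cell. They must be reconciled.
3. **The final sample**, about 30 days after the last dose and the only one after C2D1, is adequate for pre/post description but cannot distinguish resistance from withdrawal. That it is essentially off drug (5% or less remaining) rests on the assumed half-life of 1 to 7 days.

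The consequence is noisier and partly uninterpretable exploratory biomarker data. The objective response rate, the stopping boundaries and the sample size are not affected. It is worth correcting because the cost is small and the samples are irreplaceable.

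**What to change.** - In section 5.1 and calendar footnote 3, define C1D1 and C2D1 as drawn within 48 h before, and always before, the first dose of that cycle. Keep C1D8 at +/-48 h. Align the calendar's correlative row and section 2.4 with this.
- Record the draw time and the time since last dose for every sample, and use the latter in the biomarker analyses of section 8.3. This also covers delayed cycles and the variation left within a 48 h pre-dose window.
- Take the final correlative sample at the visit where progression or the decision to stop is documented, in place of the 30-day visit. Amend section 3.6 and the calendar's end-of-treatment cell to match.

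**Cost.** The same tubes and number of draws, with slightly tighter scheduling around day 1 and loss of the 30-day recovery sample. The moved sample is not a perfect on-drug sample: calendar footnote 5 places response imaging within 7 days of the start of odd-numbered cycles, so a progression draw may be up to about a week off drug. That makes it comparable in cycle phase with a pre-dose C2D1 sample, which is useful, but it reduces washout rather than removing it. Nothing in the change touches dosing.
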